4.1.3 Additional descriptive endpoints

Additional descriptive endpoints include:

- Change in quality of life (QOL) at 6 and 12 months after receiving HD Grid mapping and RF ablation relative to baseline: defined as change in quality of life assessed in validated QOL surveys (EQ-5D and AFEQT for subjects with PersAF, EQ-5D and HADS for subjects with VT)
- Rate of periprocedural and immediate post procedural (48hrs) procedure- or device- related adverse events in all subjects in whom the HD Grid is inserted (regardless of RF energy delivery).
- Rate of procedure- or device-related adverse events and cardiovascular serious adverse events in all subjects in whom the HD Grid is inserted (regardless of RF energy delivery) through 30 days post study procedure.
- Proportion of VT subjects who receive HD Grid mapping and RF energy delivery free from recurrence of sustained monomorphic VT and new or increased dose of class I/III AAD, and free from recurrence of sustained monomorphic VT on or off class I/III AADs at 12-month follow-up outside the blanking period.
- Rate of repeat ablations after study procedure during 12-month follow up defined as proportion of subjects without an additional ablation procedure to treat indicated cardiac arrhythmia (outside blanking period, if applicable).
- For subjects treated for PersAF:
 - Proportion with atypical atrial flutter (AFL) identified during procedure
 - Of those receiving HD Grid mapping and RF ablation for AFL: Utility of HD Grid specific to the identification and treatment of atypical AFL (as defined in section 4.1.2), including role of HD wave relative to along-the-spline maps in identifying ablation target(s), and time of RF application to terminate atypical AFL

5 SUBJECT SELECTION AND WITHDRAWAL

5.1 Subject Population

This clinical study will enroll male and female subjects over the age of 18 years who are indicated for cardiac RF ablation with electroanatomical mapping for the treatment of PersAF or substrate-based VT. Subjects must meet all eligibility criteria and provide written informed consent prior to conducting any study-specific procedures not considered standard of care.

Clinical Investigation Plan

5.2 Subject Screening and Informed Consent

5.2.1 Subject Screening

Members of the site's clinical study team (physician and/or research coordinator, or other delegated and qualified personnel) previously trained to this CIP must screen potential patients for clinical study eligibility based on the inclusion and exclusion criteria (section 5.3) and document the screening effort onto a site-specific Screening Log.

In case a potential patient does not meet all inclusion criteria or meets any of the exclusion criteria, the patient is considered a screening failure. The Principal Investigator or the delegated clinical investigation personnel will record the screening failure in the hospital records and on the screening log as required.

Patients who meet all inclusion criteria and none of the exclusion criteria are eligible to participate in this clinical study. Eligible patients presenting at clinical sites will be fully informed about the clinical study and asked to sign an Informed Consent form if they wish to participate in the clinical study. These patients will also be entered into the screening log.

The following assessments may need to be performed after obtaining consent and prior to the procedure, as part of the screening process:

- Pregnancy test
- Intracardiac thrombus assessment

Subject data will be collected for the clinical study after obtaining signed Informed Consent.

5.2.2 Informed Consent

A template informed consent form will be provided to each site by the Sponsor under separate cover for use in this clinical study. Site-specific language will be added to the template and approved by research personnel, the Sponsor, and governing IRB/EC prior for use in the trial.

The Investigator or his/her authorized designee will conduct the Informed Consent process, as required by applicable regulations and the center's IRB/EC. This process will include a verbal discussion with the subject on all aspects of the clinical study that are relevant to the subject's decision to participate, such as details of clinical study procedures, anticipated benefits, and potential risks of clinical study participation. Subjects must be informed about their right to withdraw from the clinical study at any time and for any reason without sanction, penalty or loss of benefits to which the subject is otherwise entitled. Withdrawal from the clinical study will not jeopardize their future medical care or relationship with the investigator.

During the discussion, the Principal Investigator or his/her authorized designee will avoid any improper influence on the subject and will respect subject's legal rights. The subject shall be provided with the Informed Consent form written in a language that is understandable to the subject and has been approved by the center's IRB/EC. The subject shall have adequate time to review, ask questions and consider participation. The Principal Investigator or his/her authorized designee will make efforts to ensure that the subject understands the information provided. If the subject agrees to participate, the Informed Consent form must be signed and dated by the subject and thereafter by the person obtaining the consent prior to any study-specific procedures. The signed original will be filed in the subject's hospital or research charts, and a copy will be provided to the subject.

Clinical Investigation Plan

Failure to obtain informed consent from a subject prior to clinical study enrollment should be reported to the Sponsor within 5 working days and to the reviewing center's IRB/EC according to the IRB's/ EC's reporting requirements.

If, during the clinical study, new information becomes available that can significantly affect a subject's future health and medical care, the Principal Investigator or his/her authorized designee will provide this information to the subject. If relevant, the subject will be asked to confirm their continuing informed consent in writing.

5.2.3 Vulnerable Populations

Vulnerable patients are defined as patients whose willingness to volunteer in a clinical study could be unduly influenced by the expectation, whether justified or not, of benefits associated with participation or of retaliatory response from senior members of a hierarchy in case of refusal to participate. Examples of populations which may contain vulnerable patients include: Individuals with lack of or loss of autonomy due to immaturity or through mental disability, persons in nursing homes, children, impoverished persons, subjects in emergency situations, ethnic minority groups, homeless persons, nomads, refugees, and those incapable of giving informed consent. Other vulnerable patients include, for example, members of a group with a hierarchical structure such as university students, subordinate hospital and laboratory personnel, employees of the sponsor, members of the armed forces, and persons kept in detention. Enrollment of vulnerable patients in this clinical study is not allowed (exclusion criterion 13).

5.3 Eligibility Criteria

5.3.1 General Eligibility Criteria

Assessment for general eligibility criteria is based on review of medical records, interview with a candidate patient, and determination by the investigator. If some of the clinical and laboratory tests required to assess eligibility are not performed as part of the sites standard of care, they must be done after written informed consent is obtained. Patients must meet ALL inclusion criteria to be considered for the clinical study. If ANY of the exclusion criteria are met, the patient is excluded from the clinical study.

5.3.2 Inclusion Criteria

1. Subject must provide written informed consent for study participation and willing and able to comply with the protocol described evaluations and follow up schedule
2. Over 18 years of age
3. Indicated for cardiac electroanatomical mapping and RF ablation procedure to treat PersAF or VT
4. Subject is diagnosed with either PersAF OR VT as defined by:
 - a. Persistent AF:
 - i. Documented symptomatic persistent AF defined as continuous atrial fibrillation that is sustained beyond 7 days but less than 12 months
 - b. VT:
 - i. Sustained monomorphic ventricular tachycardia with record of VT event within last 6 months and history of prior myocardial infarction

5.3.3 Exclusion Criteria

1. Life expectancy less than 12 months

Clinical Investigation Plan

2. Women who are pregnant or nursing
3. Known intracardiac thrombus or myxoma verified within 48 hours of index ablation procedure
4. Myocardial infarction (MI) or unstable angina, or previous cardiac surgery within 60 days of index ablation procedure
5. Percutaneous coronary intervention (PCI) within 30 days of index ablation procedure
6. Documented cerebroembolic event within the past 12 months (365 days)
7. History of valve repair, presence of a prosthetic valve, or severe mitral regurgitation thought to require valve replacement or repair within 12 months
8. Awaiting cardiac transplantation or other cardiac surgery within the next 12 months (365 days)
9. Current acute illness or active systemic infection or sepsis
10. Currently enrolled in another clinical study that could confound the results of this study
11. Any cause for contraindication to ablation procedure or systemic anticoagulation
12. Presence of other anatomic or comorbid conditions, or other medical, social, or psychological conditions that, in the investigator's opinion, could limit the subject's ability to participate in the clinical study or to comply with follow-up requirements, or impact the scientific soundness of the clinical study results.
13. Vulnerable patient or individuals whose willingness to volunteer in a study, in the judgement of investigator or public authorities, could be unduly influenced by lack of or loss of autonomy
14. Indication-specific exclusion criteria including:
 - a. PersAF:
 - i. PersAF felt to be secondary to electrolyte imbalance, uncontrolled thyroid disease, or reversible or non-cardiac cause.
 - ii. LAD > 55 mm (parasternal long axis view)
 - iii. LVEF < 40%
 - iv. Uncontrolled heart failure or NYHA function class III or IV
 - v. Presence of implanted ICD/CRT-D.
 - b. VT:
 - i. VT/VF thought to be from channelopathies
 - ii. Active ischemia or other reversible cause of VT
 - iii. Incessant VT at time of procedure
 - iv. Implanted with a ventricular assist device (VAD) (e.g. TandemHeart)
 - v. Chronic NYHA Class IV heart failure
 - vi. Ejection fraction < 15%

Incessant VT is defined as continuous sustained VT that promptly recurs despite repeated intervention for termination over ≥ 3 hours.

5.4 Subject Enrollment

A subject is considered enrolled in the clinical study from the moment the patient provides written informed consent, has been confirmed to meet all inclusion criteria and none of the exclusion criteria, and the HD Grid catheter is inserted.

5.5 Subject Withdrawal

Each enrolled subject shall remain in the clinical study until completion of the required follow-up period; however, a subject's participation in any clinical study is voluntary and the subject has the right to withdraw at any time without penalty or loss of benefit. Subjects will be requested to specify the reason

Clinical Investigation Plan

for the request to withdraw. The investigator must make all reasonable efforts to retain the subject in the clinical study until completion of the clinical study.

Conceivable reasons for discontinuation may include, but not be limited to, the following:

- Subject death
- Subject voluntary withdrawal
- Subject lost-to follow-up as described below

The Sponsor must be notified of the reason(s) for subject discontinuation. The site will provide this information to the Sponsor. Investigators must also report this to their respective IRB/EC as defined by their institution's procedure(s).

No additional follow-up will be required or data recorded from subjects once withdrawn from the clinical study, except for the status (deceased/alive) for up to 30 days post-withdrawal.

5.5.1 Lost-to-Follow-up

If the subject misses any scheduled follow-up visit, attempts at contacting the subject as detailed below will be made within the follow-up visit window. If a subject misses the 6-month follow-up visit it will be considered a missed visit. If the attempts at contacting the subject detailed below are unsuccessful for the 12-month visit, then the subject is considered lost-to-follow-up. Site personnel shall make all reasonable efforts to locate and communicate with the subject (and document these efforts in the source documents), including the following, at each contact time point:

- A minimum of two telephone calls on different days over the specified follow-up windows to contact the subject should be recorded in the source documentation, including date, time and initials of site personnel trying to make contact.
- If these attempts are unsuccessful, a letter (certified if applicable) should be sent to the subject.

[REDACTED]

[REDACTED]

[REDACTED]

[REDACTED]

[REDACTED]

[REDACTED]

[REDACTED]

Clinical Investigation Plan

6 TREATMENT AND EVALUATION OF ENDPOINTS

The Principal Investigator is responsible for ensuring all clinical study data is collected as outlined in this CIP. However, other site personnel may obtain data to be used in the trial. Physical exams and adverse event assessment may be performed by an investigator, physician, or mid-level provider (i.e. nurse practitioners, physician assistants, or fellows).

6.1 Baseline Visit

6.1.1 Baseline/Pre-procedure Clinical Assessments

The assessments listed below will be collected from each subject at the Baseline Visit. Information gathered at this visit may be used to verify eligibility of the subject for the trial.

- Documentation of the informed consent process
- Confirmation of enrollment criteria, including pregnancy test if patient is a female of child bearing potential
- Subject demographics
- Complete physical exam including height, weight, 12-lead ECG and NYHA assessment (If these assessments were performed prior to consent, they may be used if they were completed within 60-days of the ablation procedure)
- Echocardiography results (LVEF and LAD assessments) or other means of assessing LVEF and LAD (If these assessments were performed prior to consent, they may be used if they were obtained within 6-months of the ablation procedure)
- Cardiovascular disease history (most recent value prior to baseline visit)
- Arrhythmia history including documentation of PersAF or VT diagnosis (as described in the inclusion criteria)
- Antiarrhythmic medication – including any current class I/III AAD and dose, and history of any class I/III AAD and maximum dose
- Current anticoagulant medication
- Completion of the EQ-5D/AFEQT (for subjects with PersAF) or EQ-5D/HADS (for subjects with VT) questionnaires

Record the required information on the appropriate CRFs. Any protocol deviations (refer to Section 10.5 for details) observed will also be recorded at this time.

Clinical Investigation Plan

6.2 Procedure Visit

The procedure should be performed according to the IFU of the HD Grid mapping catheter, EnSite Precision™ Cardiac Mapping System, and any other medical devices used during the procedure. Physicians performing electroanatomical mapping and ablations must be qualified operators and trained on the study. Each physician who ablates during a particular case needs to be documented on the Procedure CRF.

The following information will be collected during the Procedure Visit:

- Antiarrhythmic medications- any current class I/III AAD and dose
- Anticoagulant medications
- Subject cardiac rhythm when they enter the EP lab
- Subject cardiac rhythm during mapping
- Mapping and ablation tools used during the procedure
- Procedural characteristics (set up and timing)
- Fluoroscopy time
- Mapping time (total time to collect mapping data and time for each map created/ retrospectively generated)
- Mapping points collected and used for each map created/ retrospectively generated
- Mapping location(s)
- Electrode configuration used for clinical electroanatomical mapping
- Map type(s) (i.e. Voltage, LAT, CFE, etc.)
- AutoMap settings used (if applicable)
- Arrhythmogenic substrate identified
- Field Scaling use
- Standard and HD Wave map comparisons
- Ablation strategy
- AutoMark settings used (if applicable)
- Cardioversions performed during procedure
- Attempt(s) at induction of arrhythmia as applicable before and after RF delivery
- Subject rhythm after completion of procedure

The entire case (procedure) must be recorded and stored on a study-specific USB (password-protected), provided by the Sponsor, and returned within a reasonable timeline to the Sponsor.

Protocol deviations (refer to Section 10.5 for details) that were observed during the procedure, which include any device used off-label during the procedure, will also be recorded at this time.

6.2.1 Pre-procedure thrombus assessment

Thrombus assessment is required before procedure and will be performed per investigator's standard of care. If a thrombus is discovered, the procedure should be postponed and the subject placed on anticoagulation until the thrombus is resolved and confirmed by imaging. The subject will not need to be re-consented for the study after the thrombus resolves, provided that the subject continues to meet all eligibility criteria and will undergo an RF ablation procedure unless otherwise indicated by the governing IRB/EC. Baseline visit information should be verified and updated as necessary.

Clinical Investigation Plan

6.2.2 Electroanatomical mapping

The HD Grid Mapping catheter must be used with EnSite Precision to generate a baseline electroanatomical map prior to ablation procedure. Complete contact with the cardiac wall should be achieved before collecting data. Mapping will be done per investigator discretion and is recommended to use an HD Wave electrode configuration for catheter set-up (see Appendix V). Additional maps may be created or retrospectively generated using TurboMap per physician standard practice for diagnostic purposes.

For comparison of HD wave and along-the-spline electrode configuration maps, any HD Wave configuration map used during the case should also be generated using the along-the-spline electrode configurations, preferably using TurboMap with the same geometry as baseline map (see Appendix V for details on configuration and transitions between map types). This may be done during the diagnostic procedure as part of standard of care procedure flow for relevant comparisons prior to ablation strategy determination. If not performed during the procedure, this should be performed after completion of the ablation procedure for comparison of maps resulting from different electrode configurations. Similarly, any along-the-spline electrode configuration map used during the procedure should have a comparable HD Wave configuration map generated for comparison.

For the purposes of this protocol, creating a map or mapping, is considered to be the process of collecting electroanatomical data points within heart via movement or positioning of the mapping catheter within the heart.

A retrospective map will be defined as the generation of a map that does not require collection of any new or additional electroanatomical data points but instead reuses already collected mapping data with new point collection or acquisition settings or electrode configurations selected (via TurboMap) or manual alteration of a copied open map.

Information related to each map generated, and comparison of any HD wave and respective along-the-spline maps will be reported on the appropriate CRF.

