4.1.2 Utility Objective

The second objective is to quantify and characterize the use of HD Grid and EnSite Precision with HD Wave in the electroanatomical mapping of PersAF or VT in real-world clinical settings.

Use of HD Grid and EnSite Precision with HD Wave will be quantified and characterized through the summary of the following:

- Overall procedure time: defined as time from initial catheter insertion to final catheter removal.
- Radiofrequency (RF) time: defined as duration of time RF energy is delivered
- Fluoroscopy time: defined as total time subject is exposed to fluoroscopy
- Mapping time associated with mapping arrhythmia: defined as the total cumulative mapping time and mapping time for the creation of each map (including any new or retrospective map created with Manual, AutoMap, and TurboMap mapping)
- Number of mapping points collected: defined as total number of mapping points collected for the creation of each map
- Number of mapping points used: defined as the total number of mapping points used in each map
- Number of used mapping points per minute: defined as the total number of mapping points used divided by the relative mapping time
- Substrate characteristics identified: for each type of arrhythmogenic substrate this will be defined as the frequency of substrate type identified in cases that attempted to identify the specific substrate

Clinical Investigation Plan

- Ablation strategy(s) used: defined by both the type of map used to define ablation strategy and the frequency each ablation strategy/target was used by physicians
- Role of HD Wave map relative to along-the-spline map in ablation strategy decision: as assessed by physician survey comparing maps generated with HD Wave electrode configuration to along-the-spline electrode configurations.
- Maneuverability of HD Grid catheter: defined as the ability to maneuver the HD Grid to each specified anatomic location if attempted, the ability to contact cardiac tissue, and the incidence of induced ectopic beats during maneuvering
- HD Grid electrogram quality relative to ablation catheter electrograms: defined as the proportion of electrograms collected with HD Grid that have better quality/less noise than electrograms collected with the ablation catheter at the same cardiac location as assessed by physician survey

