Create a baseline geometry and map (at a minimum, collect baseline voltage map, other maps may be collected per standard of care) of the ventricle(s) using HD Grid with HD Wave electrode configuration. Create or retrospectively generate any additional electroanatomical maps (may include generation of maps with along-the-spline configuration, preferably using TurboMap with same geometry; see Appendix V). Use the voltage HD Wave map, and/or other maps as clinically necessary to identify ablation target(s). Use ablation catheter per IFU to perform ablation per standard of care. Attempt to re-induce any VT ablated if possible. Assess acute procedural success. Create post-ablation voltage map or collect additional maps and perform additional ablation if clinically necessary.

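### The HD Wave versus along-the-spline comparison may pair maps built from different recorded points, so the endpoint can mix re-mapping with electrode configuration

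*Combined protocol and SAP*

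**What the plan says.** Section 4.1.2 lists, as one of twelve utility summaries, the role of the HD Wave map relative to the along-the-spline map in the ablation strategy decision, "as assessed by physician survey comparing maps generated with HD Wave electrode configuration to along-the-spline electrode configurations". Section 4.1.3 carries the same comparison into PersAF subjects who are mapped and ablated for atypical flutter.

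Section 6.2.2 says how the pairs are made:

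- Starting from HD Wave: "any HD Wave configuration map used during the case should also be generated using the along-the-spline electrode configurations", and this is done "preferably using TurboMap with the same geometry as baseline map".
- Timing: the second map may be made before the strategy is chosen. "If not performed during the procedure, this should be performed after completion of the ablation procedure".
- Starting from along-the-spline: such a map "should have a comparable HD Wave configuration map generated for comparison". TurboMap, geometry and data source are not mentioned here.

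Section 6.2.3.1 (for PersAF and again for atypical flutter) and Section 6.2.3.2 (VT) say that additional maps may be created or retrospectively generated, and that these "may include generation of maps with along-the-spline configuration, preferably using TurboMap with same geometry".

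Section 6.2.2 also defines two terms. Creating a map means collecting points by moving or positioning the catheter. A retrospective map is one that "does not require collection of any new or additional electroanatomical data points but instead reuses already collected mapping data".

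**The concern.** The survey answer says something about HD Wave only if the two maps being compared differ in electrode configuration and in nothing else that matters. If the comparator comes from a second pass of the catheter, the physician is also comparing two acquisitions. Section 1.1.1 itself names wavefront direction, catheter orientation and proximity to tissue among the influences on electrogram amplitude, and all of these can change between passes.

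The same section says that the effect of this catheter and configuration on ablation strategy is unknown. The comparison in Sections 4.1.2 and 4.1.3 is the only listed endpoint that sets HD Wave against another configuration, so it is the one that speaks to that question. Reporting it descriptively does not remove the confounding: a percentage with a confidence interval is still a percentage of mixed comparisons.

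**Working it through.** The plan gives no figure for this comparison, so there is nothing to reproduce. The check is of the text, followed by a bound.

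**Step 1. Does asking for a map to be generated already rule out new points?** No. The opening sentence of Section 6.2.2 uses the same verb for the baseline map, which is made with the catheter in the heart. Section 6.2.3 places along-the-spline maps among those that may be either created or retrospectively generated, and creating means collecting points. The word preferably also shows that another route is expected.

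**Step 2. Which routes to a comparator does the visible text allow?**

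| Route | Allowed by | Same recorded points? | What can differ besides configuration |
|---|---|---|---|
| TurboMap from collected data, at any time | Section 6.2.2, preferred | Yes | Settings, unless Appendix V fixes them |
| Manual alteration of a copied map | Section 6.2.2, definition of a retrospective map | Yes | The manual edits |
| New points collected before RF | Sections 6.2.2 and 6.2.3, not excluded | No | Position, contact, wavefront, possibly rhythm |
| New points collected after RF | Section 6.2.2, not excluded | No | As above, plus lesions where the counterpart map predates them |

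The last two routes are the problem. For the reverse direction the text does not state even a preference among the routes.

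**Step 3. How large could the effect be?** Suppose the survey answer is summarised as a proportion. Let f be the share of pairs not made from the same recorded points. Let d be the change in that proportion, among those pairs, caused by the new points.

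Shift in the reported proportion = f × d, and |d| ≤ 1, so |shift| ≤ f.

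For assumed values f = 0.10, 0.25 and 0.50, the ceiling is 10, 25 and 50 percentage points. The actual shift would be smaller, and d may have either sign. The documents give neither f nor d, so these are ceilings and not estimates.

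**Step 4. Could unmatched pairs be found afterwards?** Partly. Section 6.2 collects mapping time and points for each map created or retrospectively generated, AutoMap settings where applicable, and a recording of the whole case. Section 6.2.2 has map information and comparisons entered on the CRF. No visible text asks whether a pair shares its recorded points, or says how pairs that do not are analysed.

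**The case against.** The strongest reply is that the preferred route is the right one and most sites will probably follow it. The comparison sentence names only one change, the electrode configuration. Section 15 says that the study needs no procedures beyond what could be considered standard of care, which fits poorly with extra catheter passes for comparators. The recordings would probably let the sponsor regenerate matched pairs later, and the CRFs are under separate cover (Appendix II), so the flag may already exist. All of this makes unmatched pairs less likely and easier to repair. It does not exclude them, and the plan does not say what happens to them.

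Three stronger readings are tempting, and the documents do not support them.

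- *Settings may differ within a pair.* A reader might infer this because a retrospective map "reuses already collected mapping data with new point collection or acquisition settings or electrode configurations selected". That is a general definition with alternatives joined by *or*. It does not say that paired maps may differ in settings. Section 6.2.2 refers to Appendix V for configuration and transitions between map types, and Appendix V is redacted in the public copy, so it may fix them. Section 1.1.1 links HD Wave to AutoMap best duplicate, and the visible text does not say whether the along-the-spline map uses it. This is a matter to confirm and not a shown gap.
- *Comparators made after ablation carry lesions.* This is true only if new points are collected after RF. A later TurboMap regeneration of a pre-ablation map reuses pre-ablation points and carries no lesion effect.
- *This is the only within-subject contrast in the study.* It is not. Section 4.1.2 also compares HD Grid with ablation-catheter electrograms at the same location, and Section 4.1.3 has change in quality of life from baseline.

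**Conclusion.** The point holds in this form: reuse of the same recorded points and geometry is preferred in one direction and not mentioned in the other, so a site can follow the plan and still supply pairs that differ by acquisition as well as configuration. The endpoint on the role of HD Wave, and its atypical flutter version, can then mix the two.

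The effect is limited to the interpretation of this comparison. Section 8.2.2 plans no hypothesis tests, so no error rate, power or sample size changes. The numerical size is unknown and is bounded only by the share of unmatched pairs. It would be wrong to conclude that the comparison is uninformative, since pairs made by the preferred route with matched settings would be sound.

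The conclusion rests on the visible body text. If Appendix V makes same-data regeneration mandatory, the body sections still need to be aligned with it.

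**What to change.** 1. In Sections 6.2.2 and 6.2.3, replace the preference with a requirement, in both directions: the paired map is regenerated by TurboMap from the same recorded points and geometry as its counterpart, changing only the electrode configuration and any setting that defines it.
2. Do not restrict this to pre-ablation data. Section 6.2.2 asks for a comparator to any HD Wave map used in the case. Atypical flutter maps and maps made after initial ablation can be perfectly matched on their own recorded data, and a pre-ablation rule would discard them.
3. Confirm that Appendix V fixes the remaining settings, and state whether best duplicate is part of HD Wave or must be the same in both maps.
4. Flag on the CRF any pair made from newly collected points, if no such field exists.
5. In Section 8.2.2, base this endpoint and its flutter version on matched pairs, and summarise the others separately with their number.

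The cost is protocol wording and at most one CRF field. The whole case is already recorded and TurboMap is already the preferred tool, so no catheter time is added, and maps made for clinical reasons stay at the physician's discretion. The downside is that some unmatched pairs leave this one comparison, in a number that the documents do not allow one to predict.
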